14.5 Analysis of Correlative Endpoints

The proposed studies of whether any markers are predictive or prognostic are exploratory and primarily hypothesis-generating in nature. For this reason, there will be no adjustment for multiple comparisons.

14.5.1 HSF1 and Outcome

The primary correlative objective is to test whether high nuclear expression of HSF1 nuclear localization (as assessed in archival breast tumor samples) is associated with PFS, separately in the fulvestrant only arm (i.e., the single agent arm) and the ganetespib plus fulvestrant arm (the combination arm). It is possible that the direction of the relationship between HSF1 and PFS is different in each arm, so we will test this hypothesis separately in the two arms. We hypothesize that high nuclear expression of HSF1 could be predictive of poor outcome in the fulvestrant-treated patients but could be predictive of improved outcome in patients treated with the combination of fulvestrant and ganetespib.

For the power calculations, we assume that the direction of effect could be in either direction for each of the treatment arms and we will use a two-sided test. We assume that all patients have tissue for analysis. Archival metastatic specimens will take priority over archival primary tumor, in situations when both are available. We will analyze the relationship of HSF1 (dichotomized as high positive versus low positive/negative) with a dichotomized variable for PFS (above/below median PFS calculated in each group separately). It is not known what the frequency of HSF1 high positivity is in patients with metastatic disease. However data from primary tumor specimens in the Nurses' Health Study indicate that 23% of ER+ tumors are HSF1 negative, 48% are HSF1 low, and 28% are HSF1 high. It is expected that the percent of patients with high nuclear

CONFIDENTIAL

This document is confidential. Do not disclose or use except as authorized.

expression of HSF1 in metastatic specimens will be larger than the percent of primary patients with high nuclear HSF1 expression. It is also possible that patients who develop metastases are more likely to have high nuclear HSF1 expression in their archival primary tumor specimens than are patients who do not develop metastases. So it seems justified to assume that more than 28% of the patients on this study will have high nuclear HSF1 expression in their archival specimens. We assume that the percentage of patients entered on this study who have high nuclear HSF1 expression in archival specimens will be between 30% and 50%.

In these calculations, a two-sided significance level of 0.05 is used. The minimal acceptable power is assumed to be 80%. Because of the small sample sizes, sometimes a power between 81% and 83% was the smallest attainable power that was 80% or greater.

The primary analysis for the association of high nuclear expression of HSF1 and PFS will be based on a two-sided Fisher exact test of whether HSF1 high positivity is associated with a larger or smaller percent of patients with PFS greater than the median PFS on that arm. So, if the two arms of the study have different medians, then this comparison will be based on different medians in each group. This also means that in each arm (with the possible exception of the 11 out of the 71 total patients who may be lost to follow-up or begin non-protocol anti-cancer therapy before progression), at the time of analysis all patients will have had a PFS event before the group median or else be followed for PFS at least past the median PFS on that arm. (As a further secondary analysis, we will examine the time to PFS event for HSF1 high positive and HSF1 low positive/negative patients, separately for the two arms. However, we do not now have estimates of the distribution of time to PFS that are sufficiently robust for the two arms to allow us to do power calculations on this method of analysis.)

The power tables below show the range of differences that could be detected given the assumptions above.

For single-agent arm (fulvestrant alone):

			50% have high nuclear HSF1 expression			30% have high nuclear HSF1 expression			
Total N	Rando Ratio	This Arm N	Number HSF1 high pos	Detect. Diff.	True %s PFS > Med	Number HSF1 high pos	Detect. Diff.	True %s PFS > Med	True %s PFS > Med
60	1:2	20	10	68%	84%, 16%	6	67%	97%, 30%	70%, 3%

For combination arm (fulvestrant plus ganetespib):

			50% have high nuclear HSF1 expression			30% have high nuclear HSF1 expression			
Total N	Rando Ratio	This Arm N	Number HSF1 high pos	Detect. Diff.	True %s PFS > Med	Number HSF1 high pos	Detect. Diff.	True %s PFS > Med	True %s PFS > Med
60	1:2	40	20	50%	75%, 25%	12	52%	86%, 34%	66%, 14%

CONFIDENTIAL

This document is confidential. Do not disclose or use except as authorized.

CONFIDENTIAL

This document is confidential. Do not disclose or use except as authorized.

14.5.2 Comparisons of fulvestrant and ganetespib effects in cycle 2 day 9 biopsy tumor tissue

We will collect cycle 2 day 9 biopsies (required in patients with biopsy-accessible disease, see Section 3.1.14 and Section 8.1) to assess the effect of fulvestrant alone versus fulvestrant plus ganetespib within tumor specimens. This time point for the research biopsy was chosen to allow adequate time for fulvestrant to reach steady-state levels and to permit HSP90 client proteins modulating growth and survival to be destabilized by ganetespib, thereby inducing downstream transcriptional changes.

We assume that 20% of patients entered on study will have biopsy-inaccessible disease and that biopsies will not be done on these patients. We assume that 60% of patients who undergo biopsies will have informative tissue for analysis. Therefore, we assume that 48% (0.80×0.60) of patients accrued to the trial will have tissue available for this analysis.

We will compare the expression of ER, PR, AR, EGFR, HSF1, and HER2 by immunohistochemistry (IHC) and amplification of EGFR and HER2 using fluorescence in situ hybridization (FISH) to assess the effect of fulvestrant alone versus fulvestrant plus ganetespib within tumor specimens.

For this analysis, each of the markers will be described as “positive” or “negative”. For ER, PR, AR, and EGFR, “positive” will be defined as $\geq 1\%$ nuclear staining (which includes low positive and well as high positive) and “negative” will be defined as $< 1\%$ nuclear staining. For HSF1, “positive” will be defined as either 2+ staining or 1+ staining, and “negative” as no staining or rare cells positive (Santagata et al, manuscript in preparation). For HER2, we will use the standard 0-3+ scale, where categories 0, 1+, or 2+ count as negative and category 3+ counts as positive. For EGFR and HER2 amplification, FISH ratio ≥ 2.0 will be considered positive and FISH ratio < 2.0 will be considered negative. For each of these eight biologic markers, among patients who have usable tissue from the cycle 2 biopsy, we will test whether the fulvestrant arm or the fulvestrant plus ganetespib arm has a larger percent of patients with the positive category of the marker. This will be done with a two-sided Fisher exact test with significance level of 0.05. The minimal acceptable power was assumed to be 80%. Because of the small sample sizes, sometimes a power between 81% and 84% was the smallest attainable power that was 80% or greater. The power calculations assume that overall (both treatment arms combined), between 35% and 65% of patients would be in the positive category.

The power table below shows the types of differences that could be detected between the arms, given the assumptions above. While the tests are two-sided, because there are only half as many patients on the fulvestrant alone arm as are on the fulvestrant plus ganetespib arm, the differences that have power are slightly different depending on which arm is truly associated with a larger percent of patients with positive biomarker result.

CONFIDENTIAL

This document is confidential. Do not disclose or use except as authorized.

**48% of Patients with Usable Metastatic Tissue: True Treatment Difference
in Percent of Patients with Positive Marker Detectable with *Two-Sided* Fisher Exact Test**

			50% Specimens are Positive			35% are Positive		
N	N with Tissue	Arm with More Patients with “Positive” Marker	N with Positive Marker	Detect. Diff.	True % Positive Marker Combo, Single	N with Positive Marker	Detect Diff.	True % Positive Marker Combo, Single
60	28	Combo	14	58%	71%, 13%	10	54%	55%, 1%
60	28	Single	14	59%	29%, 88%	10	58%	15%, 73%

All of the other categorical correlative objectives based on the cycle 2 biopsy or (e.g., comparing the two arms by assessing a set of genes using a Nanostring custom code set each categorized as increased, decreased, or neutral) will also be compared using a two-sided Fisher exact test, but it isn’t easy to describe the detectable difference for outcomes that have three categories rather than two categories of biomarker results. Fisher exact tests and descriptive statistics will be used to explore the relationship of biomarker results obtained from different types of specimens (cycle 2 biopsy, archival tissue, CTCs, and optional biopsies at the time of progression), both overall and within treatment arm. With only 28 patients treated on the two arms expected to have usable tissue from the cycle 2 biopsy, and with some of these patients expected to not have usable tissue from the other specimens sources, most of these comparisons will have very little power.

Exploring the relationship of PIK3CA mutations and other oncogenes and PFS in each arm separately may involve a few Kaplan-Meier curves and a few log rank tests, but with only 43 patients treated on both arms combined with a PFS event at the time of analysis, and with some of these patients not having usable biopsy tissue, this exploration may be based mostly on tables of estimated medians of time to PFS event.

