5.1.10 Cycle 3 Day 1, and Day 1 of Subsequent Cycles

- Clinic visit
- Record concomitant medications
- Vital signs (heart rate, blood pressure, and respiratory rate)
- Physical examination
- Weight (Arm B only)
- ECOG performance status
- Record AEs (using CTCAE v4 grading criteria)
- Laboratory assessments
 - Hematology: hemoglobin, hematocrit, white blood cell count with differential, platelet count

CONFIDENTIAL

This document is confidential. Do not disclose or use except as authorized.

- Serum chemistry: sodium, potassium, chloride, bicarbonate, blood urea nitrogen, creatinine, glucose (random), total bilirubin, alkaline phosphatase, ALT, AST, albumin
- Serum calcium, magnesium, phosphorus
- CEA, CA27-29, if elevated at baseline. In patients with elevated markers at baseline, tumor markers should subsequently be drawn once every 2 cycles.
- 12-lead ECG (Arms B and C only). If pre-dose QTc >470 ms a repeat ECG is required approximately 24 hours after the Ganetespib dose. See section 5.6 for additional ECG requirements for patient at moderate to high risk of torsades de pointes.
- Radiologic imaging studies to evaluate tumor status. Contrast computed tomography (CT) (or without contrast if contraindicated) of chest and abdomen is preferred. Magnetic resonance imaging (MRI) of chest and abdomen is an acceptable alternative. Note: PET-CT scans are *not allowed* per protocol for primary assessment of response. PET-CT scans may be done according to clinical judgment to supplement CT or MRI scans in cases where results of the PET-CT may clarify or resolve a clinical question.
- Measurements of palpable/visible lesions, if used as a target lesion (for example, chest wall nodule)
- Follow-up imaging and measurements should be done every 2 cycles (8 weeks) and every 2-4 cycles (8-16 weeks) for patients who have been on study for >1 year. Imaging can be done +/- 1 week from targeted date but before start of the subsequent cycle.

5.1.11 Days 8 and 15 of Cycle 3 and Subsequent Cycles (Arm B only)

- Vital signs (heart rate, blood pressure, and respiratory rate)
- Weight
- Laboratory assessments
 - Hematology: hemoglobin, hematocrit, white blood cell count with differential, platelet count
 - Serum chemistry: sodium, potassium, chloride, bicarbonate, blood urea nitrogen, creatinine, glucose (random), total bilirubin, alkaline phosphatase, ALT, AST, albumin
 - Serum calcium, magnesium, phosphorus
- Ganetespib administration via silicone VADS

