A maximum of 20% of patients (n=14) on this trial may be entered on the strata for patients with non-measurable but evaluable disease (a category which includes but is not limited to patients with bone-only disease). The primary comparison will not be stratified by type of disease (measurable or non-measurable) because the stratification is being used as a mechanism to limit the number of patients with only non-measurable disease.

Based upon data from the EFECT trial, we further assume that up to 11 patients (15%) may be censored for PFS because of being lost to follow-up or receiving non-protocol anti-cancer therapy before they have progressed or died, and that this probability is not different in the two arms.⁴ To be conservative, we assume that this censoring occurs very close to the time that the patient enters the study, so the effective total sample size will be 60, with 20 patients randomized to fulvestrant alone and 40 patients randomized to fulvestrant + ganetespib.

Assuming that PFS has an exponential distribution, and that the true median PFS on Arm A (fulvestrant alone) is 4.0 months, and that accrual takes 20 months (3.5 patients per month), there will be 80% power to detect a prolongation of true median PFS to 8.0 months in Arm B (fulvestrant + ganetespib), using a one-sided 0.05 log-rank test if the patients are followed for 20 months after accrual ends (so, 40 months after accrual starts). If accrual takes only 15 months (4.5 patients per month) and follow up extends to 22 months after accrual ends, there will also be 80% power. If the true median PFS on the single agent arm is longer than 4 months, the power calculations will still be correct as long as the ratio of medians remains the same (e.g. true medians of 5 and 10 months will have the same power as the true medians of 4 and 8 months, provided that the patients are followed long enough to have the same number of expected PFS events, which is 57).

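### Low priority: the primary HSF1 analysis splits PFS at each arm's median and uses Fisher's test; a within-arm log-rank test on the same patients has clearly more power if hazards are roughly proportional

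*Combined protocol and SAP*

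**What the plan says.** Sections 1.4.1 and 14.5.1 name the association of nuclear HSF1 with PFS, tested separately in each arm, as the primary correlative objective. On the test, 14.5.1 says: "The primary analysis for the association of high nuclear expression of HSF1 and PFS will be based on a two-sided Fisher exact test". The outcome is whether a patient's PFS lies above or below the median of the patient's own arm. The power tables use 20 patients in Arm A and 40 in Arm B, with 50% or 30% HSF1-high, at two-sided 0.05 and at least 80% power.

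Time to event comes second: "As a further secondary analysis, we will examine the time to PFS event for HSF1 high positive and HSF1 low positive/negative patients", separately by arm. No test or effect measure is named. The reason given for not powering that method is that "we do not now have estimates of the distribution of time to PFS that are sufficiently robust for the two arms".

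Elsewhere the plan is less cautious. Section 14.2 begins its power calculation with "Assuming that PFS has an exponential distribution", takes medians of 4.0 and 8.0 months, and claims 80% power "using a one-sided 0.05 log-rank test if the patients are followed for 20 months after accrual ends". Section 14.5.2, on PIK3CA mutations and other oncogenes, says that exploring their relation to "PFS in each arm separately may involve a few Kaplan-Meier curves and a few log rank tests".

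**The concern.** The stated reason explains why there is no power figure for a time-to-event analysis. It does not explain why the weaker test is primary. A log-rank test needs no assumed PFS distribution, the plan already powers one on PFS for the treatment comparison, and it foresees log-rank tests for a lower-ranked marker.

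The median split loses information in two ways. A patient progressing at the first scan counts the same as one progressing just before the median, and everyone beyond the median counts alike. Fisher's test on so few patients also rejects well under 5% of the time when there is no association. In addition, 14.5.1 concedes that up to 11 of 71 patients may be censored before progression and so be exceptions to its claim that everyone can be placed above or below the median. It gives no rule for classifying them, whereas a log-rank test uses their follow-up directly.

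At stake is sensitivity: a real HSF1 association could be missed although the data would have shown it.

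**Working it through.** **1. The plan's own figures.** Inputs are the group sizes and true percentages past the median in the 14.5.1 tables. Exact power is the sum, over all pairs (a, b), of Bin(a; n1, p1) × Bin(b; n2, p2) for tables that Fisher's test rejects (0.025 in each tail).

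| Split | True % past median | Exact power |
|---|---|---|
| Arm A 10/10 | 84 v 16 | 79.8% |
| Arm A 6/14 | 97 v 30 (or 3 v 70) | 81.1% |
| Arm B 20/20 | 75 v 25 | 83.4% |
| Arm B 12/28 | 86 v 34 (or 14 v 66) | 82.4% |

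The stated power (80%, or 81-83% where that was the smallest attainable) is reproduced.

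**2. What those differences mean as hazard ratios.** With exponential PFS in each HSF1 group, HR = ln(p2)/ln(p1). In Arm A 10/10: ln 0.16 / ln 0.84 = 1.833/0.174 = 10.5. In Arm B 20/20: ln 0.25 / ln 0.75 = 1.386/0.288 = 4.8. The planned test is powered only for very large effects.

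**3. Both tests on the same simulated patients.** From 14.2: exponential PFS, whole-arm medians m of 4 and 8 months, 20 months' accrual plus 20 months' follow-up, and 20 and 40 patients. From 5.1.10: scans every 8 weeks, with progression recorded at the next scan. The HSF1 hazard ratio is my assumption (2 to 4). With a fraction f HSF1-high, the HSF1-low hazard λ solves

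f·exp(−HR·λ·m) + (1−f)·exp(−λ·m) = 0.5.

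For the unequal splits the direction follows the hypotheses in 1.4.1: HSF1-high worse in Arm A, better in Arm B. There were 40,000 runs per case. The log-rank critical value was calibrated to a true 5% from 200,000 null runs (2.05, 2.07, 2.01 and 2.02 in the order below).

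| Split | HR 2: Fisher v log-rank | HR 3 | HR 4 | True Fisher size | Log-rank size at 1.96 |
|---|---|---|---|---|---|
| Arm A 10/10 | 9 v 27% | 24 v 57% | 38 v 76% | 1.4% | 6.1% |
| Arm A 6/14 | 9 v 23% | 23 v 45-50% | 38 v 69% | 3.0% | 6.4% |
| Arm B 20/20 | 21 v 51% | 53 v 88% | 75 v 97% | 2.0% | 5.6% |
| Arm B 12/28 | 21 v 41% | 46 v 77% | 64 v 92% | 3.0% | 5.7% |

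An actual permutation p-value at HR 3 gives 56, 45, 88 and 76%, with null rejection of 5.1, 4.3, 5.7 and 4.7%. As a rough hand check, Schoenfeld's formula, z = √(d·f(1−f))·|ln HR| − 1.96, with about 34.4 events in Arm B 20/20 gives √8.6 × 1.099 − 1.96 = 1.26, or about 90%.

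**4. How much is only Fisher's small size?** At HR 3, a median-split test run at exactly 5% would have 38, 33, 66 and 53%. In Arm B 20/20 the gap is 88 − 53 = 35 points, of which 88 − 66 = 22 remain. More than half of the gap remains in every case.

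**5. Hazard ratio detectable with 80% power, Fisher then log-rank.** Arm A: 9.2 then 4.3 (10/10); 9.2 then about 5 (6/14). Arm B: 4.4 then 2.7 (20/20); 5.5 then 3.1 (12/28). The Fisher values differ from step 2 because here the split is at the sample median and scan times are tied.

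**6. Non-proportional hazards.** Section 5 lets patients who are stable or responding stop ganetespib after 6 cycles (6 × 28 days, about 5.5 months), before the assumed 8-month median. Arm B at HR 3, if the effect then ends for a share of HSF1-high patients still progression-free:

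| Share losing the effect | 20/20: Fisher v log-rank | 12/28: Fisher v log-rank |
|---|---|---|
| 0% | 53 v 88% | 46 v 77% |
| 50% | 30 v 60% | 27 v 45% |
| 75% | 20 v 40% | 20 v 27% |
| 100% | 14 v 22% | 15 v 13% |

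If the effect ends for everyone at 8 months, the figures are 39 v 44% (20/20) and 33 v 23% (12/28). If hazards reverse at the median in Arm B 20/20, Fisher wins by 44 v 12%.

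**7. Which statistic is permuted.** In the 6/14 case with HSF1-high worse, permuting the raw observed-minus-expected count gives only about 26-30% at HR 3, against 45-52% for the standardised statistic. With unequal groups the raw count moves power towards the opposite direction of effect. Permuting both statistics on the same simulated patients showed the same drop.

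**The case against.** The strongest reply is that nothing here is wrong. Fisher's test is valid, pre-specified and conservative, and its stated power reproduces. The time-to-event comparison is already planned, the marker studies are exploratory (14.5) and are to be validated later (8), so exchanging the primary and secondary labels changes little of what is reported. Choosing a primary test that can be powered from percentages alone is coherent when the hazard shape is unknown, and the exponential assumption in 14.2 concerns whole arms, not HSF1 groups. The gain rests on assumed hazard ratios and proportional hazards. Finally, recruitment was well advanced in this version (the non-measurable cohort was full by 4/30/14), so changing the test now could look post hoc.

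Much of this stands. It is a matter of efficiency, the non-proportional cases are real, and in Arm A even the log-rank test needs a hazard ratio of about 4 or more. What does not stand is the inference from missing power estimates to the weaker test: running a log-rank test requires no distribution. The post hoc objection is met by documenting the change before HSF1 results are linked to PFS.

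**Conclusion.** The point holds as a low-priority improvement. Under roughly proportional hazards, the log-rank test has about 1.7 to 2.4 times Fisher's power at a hazard ratio of 3 (77/46 in Arm B 12/28; 57/24 in Arm A 10/10), with its error rate held at 5%. In Arm B the planned test would miss about half of such associations (power 46-53%), while the same patients could reveal 77-88%.

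This rests on hazard ratios of 2 to 4 that the documents do not supply, exponential PFS with the medians in 14.2, 8-week scans, and the 30-50% HSF1-high range in 14.5.1. Allowing 16-week scans after one year changes the powers by at most about 1 point. The advantage shrinks if the HSF1 effect fades after ganetespib is stopped. It can reverse if the effect ends for nearly everyone (12/28 split) or if hazards cross. The treatment comparison is unaffected.

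**What to change.** In 14.5.1:

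- Make the primary HSF1 analysis a two-sided 0.05 log-rank test within each arm, HSF1-high against low positive/negative.
- Take the p-value from permuting HSF1 labels, using the standardised log-rank statistic, because the usual 1.96 cut-off has a true size of 5.6-6.4% here.
- Report a Cox hazard ratio with 95% CI for each arm, so that later validation studies have an effect size to plan on.
- Keep the median-split Fisher test and its tables as descriptive. They remain informative if hazards are not proportional.
- Add a short table of approximate detectable hazard ratios, stating the split, direction, proportional-hazards and scan-interval assumptions.

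Date and document the change before any HSF1 result is linked to PFS. If the sponsor prefers to leave the primary test alone, the minimum is to name the log-rank test and the Cox estimate for the secondary analysis already planned. The cost is a few sentences and one table, with no extra patients, samples or visits.

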3.1 Eligibility Criteria

Participants must meet the following criteria on screening examination to be eligible to participate in the study:

- 3.1.1 Participants must have histologically confirmed invasive breast cancer that is metastatic or unresectable locally advanced. Histological documentation of metastatic/recurrent breast cancer is not required if there is unequivocal evidence for recurrence of the breast cancer.
- 3.1.2 Estrogen and/or progesterone receptor positive breast cancer, as determined by pathology from either primary or metastatic site(s). Central confirmation is not required.
- 3.1.3 HER2 negative, defined as 0-1+ by immunohistochemistry or FISH-negative (ratio < 2.2). Central confirmation is not required.
- 3.1.4 Postmenopausal women are eligible. Postmenopausal is defined as any of the following:
- Age > 60 years
 - Age > 45 with intact uterus and amenorrhea for 12 months or more
 - Follicle stimulating hormone (FSH) levels within postmenopausal range according the ranges established by the testing facility
 - Premenopausal women who have been on a GnRH agonist for at least 3 consecutive months prior to study entry are eligible. Women in this group **MUST** remain on the GnRH agonist for the duration of protocol treatment.
 - Status-post bilateral oophorectomy-After adequate healing post surgery.
- 3.1.5 Women and men, age \geq 18 years of age
- 3.1.6 Measurable disease is required. Measurable disease is defined as at least one lesion that can be accurately measured in at least one dimension (longest diameter to be recorded) as \geq 20 mm with conventional techniques or as \geq 10 mm with spiral CT scan. Bone lesions, leptomeningeal disease, ascites, pleural/pericardial effusions, lymphangitis cutis/pulmonis, inflammatory breast disease, abdominal masses identified by physical exam that are not measurable by reproducible imaging techniques, and cystic lesions are all considered non-measurable. See section 10 for details. **As of 4/30/14, the evaluable/non-measurable cohort has been filled and only patients with measurable disease are allowed moving forward. Prior to 4/30/14, up to 20% of patients entered on this trial (i.e. 14 patients) were entered with evaluable but nonmeasurable disease.**

CONFIDENTIAL

This document is confidential. Do not disclose or use except as authorized.

3.1.7 Endocrine resistant breast cancer, defined as either:

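### The cycle 2 power table assumes 35-65% positive for all eight markers, but entry is limited to HER2-negative disease, so its stated power does not hold for HER2 IHC or HER2 FISH

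*Combined protocol and SAP*

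**What the plan says.** Entry (Section 3.1.3) is restricted by HER2 status on a local result: "HER2 negative, defined as 0-1+ by immunohistochemistry or FISH-negative (ratio < 2.2). Central confirmation is not required".

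Section 14.5.2 then treats HER2 as a cycle 2 outcome in two ways. For IHC the recorded scale is dichotomized, "where categories 0, 1+, or 2+ count as negative and category 3+ counts as positive". For FISH, "For EGFR and HER2 amplification, FISH ratio ≥ 2.0 will be considered positive and FISH ratio < 2.0 will be considered negative". Both belong to the set compared between arms: "For each of these eight biologic markers, among patients who have usable tissue from the cycle 2 biopsy", the plan tests which arm has the larger percent positive. "This will be done with a two-sided Fisher exact test with significance level of 0.05".

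The sizing rests on a single statement: "The power calculations assume that overall (both treatment arms combined), between 35% and 65% of patients would be in the positive category". The table that follows uses 28 patients with tissue, has columns for 50% and 35% positive, and is built to a minimum of 80% power, with 81-84% attained in some cases. No marker is exempted and no HER2 rate is given. The later remark in the same section about very little power concerns comparisons between specimen types, not this comparison between arms.

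**The concern.** A cohort selected to be HER2-negative can contribute a HER2-positive cycle 2 biopsy only by limited routes: the tumor has changed, the unconfirmed entry result was wrong, the either/or wording of 3.1.3 let in a FISH-negative tumor with a higher IHC score, or the FISH ratio lay between the two cuts. None of these suggests a rate near one third. If the rate is close to zero, a test on percent positive has almost nothing to compare, and the power the plan states does not describe it.

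The IHC cut adds a second difficulty. Sections 2.1 and 2.4 list HER2 among the HSP90 client proteins that ganetespib is expected to deplete. Most entrants will score below 3+, so a fall from 2+ to 1+ or from 1+ to 0 leaves the 3+ indicator unchanged.

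The two FISH cuts also differ. A ratio from 2.0 to below 2.2 is negative for entry and positive as an outcome, so a tumor can be counted as amplified at cycle 2 with no change at all.

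At stake is the interpretation of two exploratory markers measured on required research biopsies. A null HER2 result would be uninformative.

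**Working it through.** **Inputs.** From 14.2: effective sample size 60, as 20 on fulvestrant alone (Arm A) and 40 on the combination (Arm B). From 14.5.2: 48% with usable tissue, 28 biopsies, two-sided Fisher test at 0.05, 35-65% positive. Assumed, because the documents give no figure: the HER2-positive rate at cycle 2 (5%, 10% and 20% are shown) and the split of the 28 by arm (Arm A/Arm B 8/20, 9/19 and 10/18 are shown).

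**1. The plan's own figures reproduce.** 60 × 0.48 = 28.8, stated as 28. Power is the sum, over all pairs of counts (a, b) with Fisher p at most 0.05, of Bin(a; n_A, p_A) × Bin(b; n_B, p_B). For the four tabled scenarios:

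| True % positive (Arm B, Arm A) | 8/20 | 9/19 | 10/18 |
|---|---|---|---|
| 71, 13 | 82.3% | 84.6% | 86.3% |
| 29, 88 | 84.1% | 86.5% | 88.0% |
| 55, 1 | 83.3% | 89.0% | 92.5% |
| 15, 73 | 81.3% | 82.6% | 85.7% |

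Every entry exceeds 80%. The 8/20 split matches the stated 81-84% band. Only 10/18 makes the tabled percentages add up to 14 and 10 positives (for example, 18 × 0.55 + 10 × 0.01 = 10.0). The plan does not settle the split, so all three are carried forward.

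**2. What 35% requires for HER2.** 28 × 0.35 = 9.8, so about 10 HER2-positive biopsies among patients selected as HER2-negative. With a true rate q in both arms, P(at least 10 of 28) is 0.0000006 at q = 5%, 0.0002 at 10% and 0.04 at 20%.

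**3. What significance requires.** With no positives in Arm B:

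| Positives in Arm A | 8/20 | 9/19 | 10/18 |
|---|---|---|---|
| 2 | p = 0.074 | p = 0.095 | p = 0.119 |
| 3 | p = 0.017 | p = 0.026 | p = 0.037 |

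So at least 3 are needed under every split. If instead all positives are in Arm B, the minimum is 9, 8 or 7 respectively.

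**4. Power at low HER2 rates.** With Arm B at 0%, power is P(X ≥ 3) for X ~ Bin(n_A, q):

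| Assumed rate in Arm A | 8/20 | 9/19 | 10/18 |
|---|---|---|---|
| 5% | 0.6% | 0.8% | 1.2% |
| 10% | 3.8% | 5.3% | 7.0% |
| 20% | 20% | 26% | 32% |

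For 80% power against 0% in Arm B, the Arm A rate would have to be about 46%, 42% or 38%.

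The other direction is no better. If Arm A is at 5% and Arm B at 20%, power is 0.7%, 1.5% and 3.2%.

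**5. What the ordinal IHC score could show.** Suppose only scores 0 and 1+ occur. The 3+ indicator is then zero in both arms, and its power is nil whatever the shift. An exact Wilcoxon test on two levels reduces to Fisher's test on 1+ versus 0. If 50% of Arm A and 30% of Arm B score 1+ (assumed), power is 13-15% across the splits. If 80% and 20% do (assumed), it is 84-88%. The score can register a large shift that the 3+ cut cannot, but not a small one.

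**The case against.** The strongest reply is one of scale. Section 1.4.2 makes these comparisons exploratory, Section 14.5 applies no multiplicity adjustment for that reason, and the table is offered conditionally on its assumptions. It stays usable for any marker that does fall in 35-65%. All of that stands, and it makes this a minor point. It does not remove the mismatch, because the plan applies the assumption to every one of the eight markers.

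Four stronger readings are tempting, and the documents do not support them.

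- A reader might infer that ganetespib should push HER2 FISH down from its floor. Sections 2.1 and 2.4 speak of degrading client proteins. Nothing there says that gene copy number falls, and Section 8 raises HER2 amplification as a possible resistance mechanism, which would be a gain. The 0% in Arm B used above is therefore an arithmetic scenario for FISH, not a predicted drug effect.
- A reader might infer that the differing FISH cuts undermine the analysis of HER2 amplification in baseline CTCs and PFS. That is a baseline association in a different specimen, where acquired versus pre-existing status is not the question.
- A reader might infer that every positive FISH count is contaminated. Section 1.4.2 also tabulates FISH in archival tissue, so a pre-existing ratio from 2.0 to below 2.2 can be recognized where an archival result exists. The number of such patients is unknown, and a research cut that differs from an eligibility cut is not in itself an error.
- A reader might infer that a null HER2 result will be reported as no effect. The plan prescribes no such reading. The risk is only that nothing warns against it.

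**Conclusion.** The stated power does not hold for two of the eight cycle 2 markers, HER2 IHC and HER2 FISH. At assumed rates of 5%, 10% and 20% in Arm A and 0% in Arm B, it is about 1%, 4-7% and 20-32%, against 84-88% in the plan's own scenario of 88% versus 29%. The result depends on an assumed HER2 rate and an assumed split of the 28 biopsies. The conclusion is the same under all three splits and would change only if HER2 positivity came close to the plan's 35% lower bound, for which the documents give no support. The floor is near zero, not exactly zero. The other six markers, PFS and the secondary clinical endpoints are untouched. Severity: minor.

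**What to change.** In Section 14.5.2:

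1. State that the 35-65% assumption and the power table do not apply to HER2 IHC or HER2 FISH.
2. Compare the recorded HER2 IHC score (0, 1+, 2+, 3+) between arms with an exact Wilcoxon or trend test.
3. Report the HER2 FISH ratio descriptively by arm, and list any conversions to 3+ or to a ratio of at least 2.0, without presuming that ganetespib lowers copy number.
4. Where an entry or archival FISH ratio exists, flag tumors from 2.0 to below 2.2 and do not count them as acquired amplification. This cannot be done for everyone, since 3.1.3 does not require a ratio when IHC is 0-1+.

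It would also help to state the expected split of the 28 biopsies by arm.

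The cost is SAP wording: the cycle 2 score and ratio must already be obtained to apply the planned cuts. The small downside is that the HER2 IHC result becomes a shift in score instead of a percent positive, and power for small shifts stays low.
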